Data analysis: Our primary analysis will be to compare the combined intervention arms (SCC1 & SCC2) against the usual care control to assess the effects of integrating SCC into FP services, and then compare the outcomes between the two intervention arms to determine whether the more intensive SCC1 shows a larger effect than the less intensive SCC2. The primary outcome-- correct use of contraception/SCM (depending on pregnancy intention)-- will be represented as a binary variable as defined in D.2.3.5, but we will also explore a categorical or continuous outcome derived from frequency of correct use throughout the study. Secondary outcomes to be investigated are pregnancy status, PMTCT use, consistent condom use, and seroconversion of partner. We will use an intent-to-treat approach in the primary analyses; secondary analyses will use only study completers. Participants remain in the study and analysis regardless if their relationship status changes during the study. Attrition weights will be used to account for dropouts, and analyses will incorporate design effects from this weighting in the calculation of standard errors and tests of significance. We will account for clustering, and with only 9 clusters/clinics we will conduct individual level analysis. Regression methods can directly model correlations among units in a cluster (random effects or multilevel models) or more simply adjust standard errors for clustering (GEE, robust standard errors), but these approaches are not reliable with so few

clusters,⁷⁵ so we'll use standard regression methods, but rather than attempt to estimate ICC directly, we will explore the sensitivity of significance levels using a range of plausible ICCs values for the outcomes.

Aim 1: Assess intervention effect on contraception/SCM use: *Hypothesis: Both SCC1 and SCC2 will be superior to usual care, and SCC1 will be superior to SCC2 regarding the primary outcomes.* We'll use logistic regression to compare rates of contraception or SCM use (depending on pregnancy intention) in the SCC1 and SCC2 interventions compared to the control condition, and investigate differences between SCC1 and SCC2 in a separate regression. The models will include covariates to adjust for baseline variables (e.g., childbearing stigma, age, sex) that may differ at baseline and to increase precision of the estimates.

Aim 2: Assess intervention effect on secondary outcomes (pregnancy status; PMTCT use, consistent condom use, partner seroconversion): We will use the same analytic strategy as described for Aim 1.

Aim 3: Examine eIMB moderators and mediators of intervention effects on SCM and contraception use. We will identify bivariate correlates of the primary outcome from among baseline variables using correlation coefficients, t-tests and chi square tests, followed by a stepwise regression approach to identify a parsimonious list of predictors. We will then use longitudinal analyses to investigate changes in the primary outcome relative to changes in dependent variables such as SCM knowledge, motivation and self-efficacy. Like the baseline cross-sectional analysis described above, we will start with bivariate analyses that will inform a subsequent stepwise regression approach. We will use clinic fixed effects, because with only 9 clinics, clustering standard errors to correct for correlation between patients in the same clinic would significantly reduce power. Robust estimation techniques can adjust for correlation in multiple observations of a given patient over time. We will use a similar analytic approach to examine determinants of the secondary outcomes. Lastly, we will investigate the paths through which the intervention works, and subgroups that benefit more from the intervention. E.g., male clients and their partners may use contraception/SCM more because of their greater control over decision making and ability to secure partner participation in SCC. We can test this hypothesis by adding an interaction term between gender and the intervention. Using methods described by MacKinnon⁷⁶ and others,^{77,78} we will assess whether the intervention has a direct impact on contraception/SCM use or mostly though a mediating variable such as communication with provider about childbearing needs (which may result in clients being more apt to receive the information and encouragement needed to use SCM/contraception).^{46,79}

Aim 4: Cost-effectiveness analysis. We will track all costs associated with implementing SCC1 and SCC2 beyond those of existing FP services (the costs of which we will also measure), such as labor costs associated with SCC sessions and consults with FP nurses, supervision of the FP nurses (in SCC1), contraceptives and SCM client kits, and cost of intervention materials (posters, SCM instructional videos). Labor costs are based on clinic-specific data, external sources, and our own documentation (e.g., # and length of SCC sessions, FP consults, supervision meetings). Fixed costs will be allocated to the intervention as the fraction of time the premises are used for the intervention (e.g., SCC sessions). Training materials and supplies will be costed at purchase prices. Development costs such as personnel costs for the SCC training workshop will be differentiated from ongoing operational costs, but will exclude research costs (e.g., surveys). We will also evaluate potential efficiencies in operational costs (SCC sessions and ongoing supervision) over time and differentiate between the fixed costs of the intervention and the marginal cost of adding an additional client to inform generalizability to other settings. The analysis will be performed from the clinic perspective as we cannot accurately incorporate costs incurred by the client (e.g., lost earnings on clinic visit days), but the coordinator will track the number and duration of SCC sessions, and the survey will assess transportation and other client costs. We will assess whether the intervention is cost-effective by assessing the cost-effectiveness ratio (CER), defined by the difference in per-capita cost of the two intervention models relative to the control. We will assess average overall and marginal cost per achieved pregnancy (without partner seroconversion) or prevented pregnancy (depending on the patient's desired pregnancy status) and compare those to published values such as Shade et al.⁸⁰ We will estimate confidence intervals for our CERs using bootstrap methods.⁸¹

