STUDY PROTOCOL
May 1, 2017

Project Title: Integrating Safer Conception Counseling to Transform HIV Family Planning Services

NCT03167879

Registered on clinicaltrials.gov on 5/23/17

STUDY PROTOCOL

Overview. This 3-arm, cluster RCT will compare two models for implementing a comprehensive FP program that integrates SCC within current FP services in HIV clinics—an up to 6-session, multi-component, structured SCC intervention (SCC1), and a workshop to train FP providers on use of SCC guidelines (SCC2)—versus existing FP services (usual care). Both SCC1 and SCC2 will use routine screening for fertility desires and a workshop for training FP nurses to implement SCC, but SCC1 is differentiated by its use of a structured counseling SCC protocol and manual (as opposed to the clinical acumen of the trained FP nurses), and inclusion of client outreach and ongoing supervision support. Each arm will be implemented at 2 sites (6 sites in total) and each site will enroll 65 clients (total n=390) with serodiscordant partners who have childbearing desires at recruitment. Participants will be surveyed at baseline, months 6 and 12, and post-pregnancy for those who become pregnant prior to month 12. The primary outcome is correct use of SCM or contraception (depending on desired pregnancy status following SCC consult); secondary outcomes are pregnancy status, PMTCT use (if pregnant), partner seroconversion, and condom use. A cost-effectiveness analysis will also compare the 3 arms to inform policy and practice recommendations for settings of various resource levels.

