able to successfully use SCM when the partner did not attend. The proposed study will provide data to answer this important question. In our pilot, most female partners attended SCC, but if not, she will be given a referral (via the male client) to come to TASO or the hospital FP clinic for contraception if they decide against childbearing; or if seeking childbearing the male will be asked to report on the timing of his partner's fertile period with information from his partner, or the nurse will phone the partner for this information with consent from the male. After conception, the FP nurse will provide PMTCT services; if clients have a miscarriage, the cause will be addressed if possible, than contraception or further SCC offered, as desired.

SCC Introductory Consultation (45-60 minutes):

- * Build rapport and supportive environment; encourage client/couple to express needs and expectations.
- * Discuss context related to readiness for childbearing (partner HIV status; HIV disclosure; partner's fertility desire; # of existing children; health of relationship; available resources/supports; work patterns separating the couple).
- * Review HIV and health risks of childbearing for mother, infant, & partner, & factors that contribute to or protect from risk (SCM; ART; CD4; PMTCT; STIs; alcohol use; nutrition). Encourage delaying pregnancy if medical condition not optimal (not on ART > 6 mos.; CD4<200; active STI) and provide treatment (for STIs, acute OIs, or ART) as needed.
- * Encourage client/couple to consider this information and take time to decide whether or not they want to have a child, and return the next week for either SCC or contraception counseling and services accordingly.

SCC Session 1 (20-30 minutes):

- * Review client/couple's decision: if no longer desire a child, provide contraception; otherwise continue with SCC.
- * Teach client to time the woman's ovulation period and fertile window using pregnancy calendar.
- * Client/couple receives instruction on selected SCM (TUI, or MSI if female HIV+ and male HIV-). Brochures and tool kit specific to the chosen method (e.g., condoms, lube, syringe, plastic cup) are given to client to take home; instructional video will be shown; SMS texts will be used to remind client of start of fertile period if they have a phone.

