This model for integrating SCC into existing FP services mimics the approach used by the MoH for infusing new services. Like SCC1, SCC2 will also use screening of childbearing desires and clients who report such desires will be encouraged to discuss this with their providers, and the triage station will record the information in the client's chart so that providers can refer the client to the FP nurses for SCC or contraception. Training of FP nurses (see Fig. 2) will be mostly educational and use role plays, but will not train on use of MI style communication with clients. A simplified manual and some (SCM instructional brochures, fertility calendar) but not all tools (instructional videos; SCM kits) produced for SCC1 will be used in SCC2. Supervision will not be provided by the study supervisors; rather, FP nurses may consult with clinic physicians and the FP clinic on the hospital campus when needed, which is the typical approach for new services. Like SCC1, SCC2 sessions will be recorded and a random selection coded for fidelity by the Project Director, but feedback will not be given to the nurses, as this is not the norm when new services are added. SCC2 is designed to reflect how new treatment advances are integrated into routine care by the MoH, and to represent a viable, less intensive alternative to the structured, multi-component SCC1, the comparison of which provides critical data to guide the MoH and other policy makers on how to best incorporate SCC into FP services. SCC sessions attended by participants will be logged and research participant surveys will assess SCC and FP services received.

Arm 3: Existing FP services (usual care control) Each study site currently provides FP services that focus on providing contraception and PMTCT care, but there's no SCC. The usual care sites will continue to provide FP services as is, with no use of routine screening of childbearing desires or SCC. Routine HIV and FP care in Uganda is unlikely to incorporate SCC during the course of this study, as SCC guidelines have been available

for years, yet SCC has remained scarce in Uganda and SSA. Also, TASO has indicated it has no plans to integrate SCC into usual care until the study ends and it sees efficacy and cost-effectiveness data.

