Recruitment. We will enroll 3-4 clients per month over 18 months at each site, which is feasible as >20 clients met this eligibility criteria in each recruitment month in our pilots. Recruitment will be stratified by sex to ensure a 50/50 gender balance, which will better enable us to examine intervention effects on partner seroconversion

and to gain the perspective of both male and female clients regarding fertility. We could enroll the sample more quickly, but the long enrollment period ensures we can recruit the target number of men, and enables us to have our 3 site coordinators manage three sites each (min. 1 day per week at each clinic) to limit personnel costs. Clients at the SCC1 and SCC2 sites who report at triage that they desire to have a child with a negative or unknown HIV status partner will be referred by triage to the site coordinator for screening. Screening (incl. partner HIV testing) and baseline survey will be completed prior to the initial SCC consultation. At the usual care site, the childbearing screening item will be included at triage only during the days of recruitment, which will be used to identify potential participants who will then be referred to the site coordinator for the same screening conducted at the intervention sites; the data from the screening item will not be placed in the client's chart or given to the FP nurse, as this screening is not part of usual care. Clients who decline to bring their partner in for HIV testing (but are otherwise eligible) and thus do not participate, will be asked to provide basic sociodemographic and partner characteristics in order to assess how they differ from the enrolled clients.

Data Collection

Assessment schedule: The baseline assessment will be done by the site coordinator once eligibility is confirmed, followed by assessments at months 6, 12, and post-pregnancy (if pregnancy occurs prior to month 12). To minimize attrition we will collect contact info (phone numbers and maps of homes), including contact information for family or friends who have frequent contact with the client. Clinic staff will also be able to help us track clients that we have difficulty reaching. In our current study we achieved 94% retention at Month 12.

Participant Compensation: Participants will receive 20,000 Ush (~\$6 USD) at each assessment.

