Measures. Assessments will include measures of the primary and secondary outcomes and variables that map to our eIMB conceptual framework for understanding use of SCM and contraception, as listed below. Survey measures have been translated into Luganda in our prior research. The survey will be interviewer-administered using computer-assisted software, and administration time is 45-60 minutes.

Primary outcome: Correct use of contraception or SCM over the past 6 months, depending on pregnancy intentions; a single binary indicator will be created for use as the primary outcome, while continuous and categorical measures of frequency and duration of use will be used in secondary analyses. Correct use of contraception is defined as always using both condoms and another modern contraceptive (e.g., oral pills, DEPO injection, IUD implant) (i.e., dual contraception) over the past 6 months (since last survey), and will be ascertained via self-report and chart review (provision of non-condom contraceptive). Male participants will be asked to consent (it won't be required) to the coordinator calling their partner on the phone to assess use of non-condom contraceptives; these data will be kept confidential from the male. This definition is consistent with FP policy and practice in Uganda,⁶⁶ as condoms are important for HIV prevention, but used too inconsistently to prevent pregnancy, hence the need for an added contraceptive. If a participant becomes single or abstinent during the course of the study, avoiding pregnancy and use of contraception will be considered the desired behavior. The primary outcome will define whether SCM or contraception use was consistent (and changed to correspond with changes in pregnancy intentions) with pregnancy intentions over the entire study period.

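### The Overview scores the primary outcome against a decision made after SCC, which usual care does not receive, and the Measures section does not say what sets intention instead

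*Combined protocol and SAP*

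**What the plan says.** The Overview gives the primary outcome as "correct use of SCM or contraception (depending on desired pregnancy status following SCC consult".

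Usual care has no such consult. Under Arm 3: "The usual care sites will continue to provide FP services as is, with no use of routine screening of childbearing desires or SCC". The Recruitment section adds that the screening item is asked at usual-care triage on recruitment days only, and that "the data from the screening item will not be placed in the client's chart or given to the FP nurse".

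The operational definition (Measures, Primary outcome) does not mention the consult. It reads "Correct use of contraception or SCM over the past 6 months, depending on pregnancy intentions", and requires that use was consistent "and changed to correspond with changes in pregnancy intentions) with pregnancy intentions over the entire study period". The power and data analysis paragraphs likewise refer to pregnancy intention without the consult.

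Two other places bear on how intention could be known. The mediator/moderator table lists self-reported childbearing desires and intentions as a survey measure. The assessment schedule places surveys at baseline, month 6 and month 12 (and post-pregnancy), with no restriction by arm.

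**The concern.** Intention decides whether a client is judged on SCM or on dual contraception, so it decides who counts as a success. Under the Overview's rule, the reference point does not exist for the 130 of 390 participants in usual care (2 sites of 65).

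Baseline intention is a poor substitute. Eligibility requires every participant to be considering childbearing, and the triage item is deliberately broad so that undecided clients are included. The plan expects half the sample to end up choosing contraception. Take a usual-care client who settles against pregnancy soon after enrolment and then uses dual contraception throughout. That client fails if judged on baseline intention, and can succeed if judged on current intention.

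Intention is also open to influence by the intervention. The description of the structured SCC sessions reports that many pilot clients decided against childbearing after the consult. A classifier that treatment can change needs to be measured in the same way in every arm. Otherwise a difference in the primary comparison can appear, or be hidden, with no difference in behaviour.

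**Working it through.** **Comparing the sections**

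| Question | Overview | Measures, Primary outcome |
|---|---|---|
| What is use judged against? | Desired status after the SCC consult | Pregnancy intentions |
| Does it exist in usual care? | No (Arm 3) | Yes, if taken from the survey |
| Are changes followed? | Not stated | Yes, over the whole study |
| Source of intention | The consult, by implication | Not stated |
| Time point within each 6-month window | After the consult | Not stated |

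The mediator/moderator table supplies a survey item that could do the job, but nothing says that it classifies the primary outcome or dates changes between surveys.

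**Inputs** (Power analysis)

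- Dual contraception among those avoiding pregnancy: 11%.
- TUI or MSI use among those trying to conceive: 15%.
- Expected split: half pursue pregnancy, half contraception, from pilot data.
- Stated usual-care rate of the primary outcome: 15%.
- Stated target difference, usual care against the combined SCC arms: 4.5 points.

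**The plan's usual-care rate.** At an even split, 0.5 × 15% + 0.5 × 11% = 7.5% + 5.5% = 13.0%. The stated 15% arises only if every usual-care client is judged on SCM.

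**Effect of the scoring rule.** Let c be the share of usual-care clients who move to avoiding pregnancy. This is an assumption: the documents give no figure for usual care. Assume also that movers do not use SCM, so they score zero if still judged on baseline intention.

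- Judged on current intention: (1 − c) × 15% + c × 11%.
- Judged on baseline intention: (1 − c) × 15% + c × 0.
- Shift: c × 11%.

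| c | Current intention | Baseline intention | Shift (points) |
|---|---|---|---|
| 0 | 15.0% | 15.0% | 0 |
| 10% | 14.6% | 13.5% | 1.1 |
| 25% | 14.0% | 11.25% | 2.75 |
| 50% | 13.0% | 7.5% | 5.5 |

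If SCC clients behaved identically but were judged on their current decision, the shift would appear as a treatment effect in favour of SCC. Intention recalled at the end of a window and fitted to what the client did would instead raise the usual-care rate. The documents give nothing from which to size that.

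**The 4.5-point yardstick.** It is the plan's own target, but its stated power does not reproduce. Usual care retains 130 × 0.9 = 117 participants, or 58.5 per site. The design effect is 1 + (58.5 − 1) × 0.01 = 1.575, so the effective number is 117 / 1.575 = 74.3, against twice that in the combined arms. For 15% against 19.5%, two-sided at 5% (the level is assumed, as none is stated), power is about 12%, not above 80%. About 17 points would be detectable at 80% power. That is a separate matter and does not bear on the definition.

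**The case against.** A reader might infer that intention is fixed prospectively in the SCC arms and is available in usual care only from baseline or by later recall. The documents do not support that.

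- The survey schedule and the listed intention item apply to all arms. Month-6 intention is therefore current in usual care and prospective for months 6 to 12. Changes between surveys are a gap, but the survey has that gap in every arm.
- No section carries a decision from an SCC session into the outcome data. The step "Review client/couple's decision: if no longer desire a child, provide contraception; otherwise continue with SCC" describes care in SCC1, not scoring. In SCC2, clients are encouraged to raise the subject and may be referred, so a consult is not guaranteed.
- Freezing intention at baseline conflicts with the Measures section, which follows changes. The 5.5-point figure therefore illustrates a rule that the plan does not state. It also borrows for usual care a 50% split drawn from pilot data, although usual care has no consult to prompt the decision.
- Keeping the triage answer out of the usual-care chart protects usual care from contamination. It does not stop the research survey from recording intention.

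All of this stands, and it limits the point. It does not remove the conflict between the two definitions or supply the missing source and time point. The month-6 survey is prospective only for the second window, while the Measures section judges the entire study period. Using intention at the start of each window as the sole rule would leave months 0 to 6 judged on baseline. Clients in any arm who then chose contraception would be failed for it.

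**Conclusion.** The point holds as a conflict in the primary outcome definition. The Overview's rule cannot be applied in usual care, and the Measures section's rule is incomplete because it names no source or time point for intention in any arm. That the arms will in fact be scored differently is a risk if the Overview is followed, not something that the plan states.

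The possible artefact in usual care runs from 0 to 5.5 points as the switching share goes from 0 to 50%. It rests on three assumptions: that share, movers judged on baseline intention, and no SCM use among movers. The upper end exceeds the stated 4.5-point target, while shares of 10% and 25% give less. The direction is not fixed, since recall fitted to behaviour would act the other way. Because this is the primary endpoint and the choice of rule changes who succeeds, it should be settled before any outcome is scored.

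**What to change.** 1. Delete the reference to the SCC consult from the Overview's primary outcome, and reconcile that sentence with the Measures section.
2. In all three arms, set intention only from the research survey already scheduled at baseline, month 6 and month 12. Ask it before any question on method use, and include when intention changed since the last survey.
3. Score use in each 6-month window against that intention, following the dated changes. This makes the existing requirement, "and changed to correspond with changes in pregnancy intentions", workable.
4. Do not use decisions recorded in SCC sessions for scoring.
5. Add a sensitivity analysis that scores months 6 to 12 against the intention stated prospectively at month 6. The main rule relies on recall for changes between surveys, and this check does not.

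The cost is a wording change, a few minutes of survey time and some recall error about when intention changed. The same instrument is used in every arm, although monthly SCC1 sessions may anchor recall better there, which is a further reason for the sensitivity analysis.
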